10.2 Documenting Enlarged Lymph Nodes

A maximum of the 6 largest nodes or nodal masses (minimum size $> 1.5 \times 1.5$ cm) will be followed for response if enlarged at baseline. Wherever possible, enlarged nodes should be documented in the nodal disease case report form and followed by CT scan.

Notes:

If a patient does not have baseline lymphocytosis of at least $10 \times 10^9/L$, he or she must have at least one node $\geq 2 \times 2$ cm on CT scan to be eligible.

For additional enlarged lymph nodes/nodal masses beyond the maximum of 6 recorded, record them as “multiple enlarged nodes” as a single entry on the nodal disease case report form. Do not list each individual non-target node or node group as separate lesions.

10.3 Documenting Organomegaly

If hepatomegaly is documented on the baseline CT scan, record as extra nodal lesion (“Liver”) on the baseline extra nodal case report form. Splenomegaly or splenic lesions on the baseline CT scan are considered nodal disease and should be recorded on the nodal case report form. At the time of follow-up CT examination, record “present” (if still enlarged or continuing enlargement seen) or “absent” (if normal size). Record “increased” ONLY if unequivocal progression of *substantial magnitude is seen (estimated 50% increase) and is believed sufficient to consider overall that the patient has progressed.*

10.4 Response

All patients will have their BEST RESPONSE from the start of study treatment until the end of treatment classified as outlined below. In patients with limited disease at study entry, response will be assessed using only parameters that were abnormal at baseline.

Complete Response (CR): CR requires all of the following criteria, maintained for a period of at least 8 weeks.

- Peripheral blood lymphocytes (evaluated by blood and differential count) $< 4 \times 10^9/L$;
- Absence of significant lymphadenopathy > 1.5 cm in diameter on physical examination and CT scan

- No hepatomegaly or splenomegaly by CT scan
- Absence of constitutional symptoms attributable to disease
- Normal blood counts above the following values:
 - Neutrophils more than $1.5 \times 10^9/L$ without need for exogenous growth factors
 - Platelets more than $100 \times 10^9/L$ without need for exogenous growth factors
 - Hemoglobin more than 110 g/L without red blood cell transfusion or need for exogenous erythropoietin.
- A marrow aspirate and biopsy should be performed to demonstrate that a CR has been achieved at the time other criteria for CR are met.
 - To define a CR, the marrow sample must be at least normocellular for age, with < 30% of nucleated cells being lymphocytes. Lymphoid nodules should be absent. If lymphoid nodules are found, they will often reflect residual disease. These nodules should be recorded as "nodular PR". Immunohistochemistry should be performed to define whether these nodules are composed primarily of T cells or lymphocytes other than CLL cells.
 - If the marrow is hypocellular, a repeat determination should be performed after 4 weeks, or when peripheral blood counts have recovered. However, this time interval should not exceed 6 months after the last treatment. A marrow biopsy should be compared with that of pretreatment marrow.
 - Optional: The quality of the CR may be assessed for minimal residual disease by flow cytometry or by immunohistochemistry (IHC).
- Patients who fulfill all the criteria for a CR (including the marrow examinations described above) but who have a persistent anemia or thrombocytopenia or neutropenia apparently unrelated to CLL but related to drug toxicity will be considered as CR with incomplete marrow recovery (CRi). A repeat bone marrow should ideally be done in these patients when counts recover fully. If the bone marrow at this time reveals no CLL, these patients will be considered as having CR at that time.

Partial Response (PR): To define a PR, at least 1 of the criteria of Group A plus 1 of the criteria of Group B must be met and persist for ≥ 8 weeks, in the absence of any criteria definitive of progressive disease.

Group A:

- A 50% or more decrease in peripheral blood lymphocytes from the value before therapy.
- A 50% or more reduction in lymphadenopathy (by CT scan) either in the sum products of up to 6 measurable lymph nodes, or in the largest diameter of the enlarged lymph node(s) detected prior to therapy.
- A 50% or more reduction in the noted pretreatment enlargement of the spleen or liver, as estimated by CT scan.

Group B:

- The blood count should show one of the following results:
 - Neutrophils more than $1.5 \times 10^9/L$ without need for exogenous growth factors or 50% improvement over baseline without need for exogenous growth factors.
 - Platelet counts greater than $100 \times 10^9/L$ or 50% improvement over baseline without need for exogenous growth factors.

- Hemoglobin greater than 110 g/L or 50% improvement over baseline without requiring red blood cell transfusions or exogenous erythropoietin.

Progressive Disease (PD): Progressive disease during or after therapy is characterized by at least one of the following:

- Progression of lymphadenopathy
 - Appearance of any new lesion, such as new enlarged lymph nodes ($> 1.5 \times 1.5$ cm), splenomegaly, hepatomegaly, or other organ infiltrates.
 - An increase by 50% or more in greatest determined diameter (= greater than 65% increase in bidimensional product) of any previously recorded measurable node.
- An unequivocal increase in the previously noted enlargement of the liver or spleen by an estimated 50% or more or the de novo appearance of hepatomegaly or splenomegaly.
- Transformation to a more aggressive histology (e.g. Richter syndrome).
 - Whenever possible, this diagnosis should be established by lymph node biopsy.
- Occurrence of cytopenia (neutropenia, anemia, or thrombocytopenia) attributable to CLL.
 - During therapy:
 - During therapy, cytopenias cannot be used to define disease progression.
 - After treatment:
 - The progression of any cytopenia (unrelated to autoimmune cytopenia), as documented by a decrease of Hb levels by more than 20 g/L (2 g/dL) or to less than 100 g/L, or by a decrease of platelet counts by more than 50% or to less than $100 \times 10^9/L$, which occurs at least 3 months after treatment, defines disease progression, if the marrow biopsy demonstrates an infiltrate of clonal CLL cells.

Note:

B cell receptor targeted drugs can mobilize CLL cells from tissues into the peripheral blood, interfering with their homing. This characteristic pharmacologic action can be prominent early in therapy, but can also persist over time. This occurrence should not be confused with PD unless the treated patient develops other CLL-related signs or symptoms of PD. In the absence of other objective evidence of PD, **lymphocytosis alone should not be considered an indicator of PD** [Cheson 2012].

Stable Disease (SD): Patients who have not achieved a CR or a PR, and who have not exhibited progressive disease, will be considered to have stable disease (which is equivalent to a nonresponse).

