10.5 Response Duration

Response duration will be measured from the time measurement criteria for CR/PR (whichever is first recorded) are first met until the first date that recurrent or progressive disease is objectively documented, taking as reference the smallest measurements recorded on study (including baseline).

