10.6 Stable Disease Duration

Stable disease duration will be measured from the time of start of treatment until the criteria for progression are met, taking as reference the smallest sum on study (including baseline).

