10.7 Progression-Free Survival

Progression-free survival (PFS) is defined as the time from study entry until disease progression or death.

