10.8 Methods of Measurement for CT-Scan Evaluation

The same method of assessment and the same technique should be used to characterize each identified and reported lesion at baseline and during follow-up as indicated in Section 9. While on study, all lesions recorded at baseline should have their actual measurements recorded at each subsequent evaluation, even when very small (e.g. 2 mm). If it is the opinion of the radiologist that the lesion has likely disappeared, the measurement should be recorded as 0 mm. If the lesion is believed to be present and is faintly seen but too small to measure, a default value of 5 mm should be assigned. For lesions which fragment/split add together the longest diameters of the fragmented portions; for lesions which coalesce, measure the maximal longest diameter for the “merged lesion”.

- 10.8.1 Clinical Lesions. Clinical lesions will only be considered measurable when they are superficial and ≥ 10 mm as assessed using callipers (e.g. skin nodules). For the case of skin lesions, documentation by colour photography including a ruler to estimate the size of the lesion is recommended. If feasible, imaging is preferred. Lymph nodes should be measured by CT scan as described in section 10.2 if followed.
- 10.8.2 Ultrasound. Ultrasound is not useful in assessment of lesion size and should not be used as a method of measurement. If new lesions are identified by ultrasound in the course of the study, confirmation by CT is advised.

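### The nodal progression rule has no minimum size, so under the nadir reference used for response duration a node of 10 mm or less can be progressive disease while still within the complete-response limit

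*Protocol*

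**What the plan says.** **PD, recorded nodes (Protocol 10.4).** PD includes "An increase by 50% or more in greatest determined diameter" of any measurable node already on record, which the protocol equates with a rise above 65% in the bidimensional product. No minimum current size and no minimum growth in millimetres is attached.

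**PD, new nodes (10.4).** A separate bullet covers "Appearance of any new lesion, such as new enlarged lymph nodes", and this one does carry a size limit, above 1.5 x 1.5 cm. Section 10.2 uses the same two-dimensional limit for choosing up to six nodes at baseline.

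**CR (10.4).** The nodal requirement is "Absence of significant lymphadenopathy > 1.5 cm in diameter on physical examination and CT scan".

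**Reference value.** For response duration, 10.5 says "taking as reference the smallest measurements recorded on study (including baseline"; the SAP repeats this for Table 13. For stable-disease duration, 10.6 says "taking as reference the smallest sum on study (including baseline", which is a sum and not a single node. Section 10.7 says only "Progression-free survival (PFS) is defined as the time from study entry until disease progression or death". The PD and PR text in 10.4 names no reference.

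**Small nodes (10.8).** Recorded lesions go on being measured at very small sizes, with 2 mm as the example. A lesion thought to have disappeared is entered as 0 mm. For one that is faint and too small to measure, "a default value of 5 mm should be assigned".

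**Surrounding rules.** PR must last at least 8 weeks with no PD criterion met (10.4). Patients who progress go off study (12.2). There is no central radiology review (13.1).

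**The concern.** A purely relative threshold applied to a nadir becomes very small in absolute terms once a node has shrunk well. A node can then be PD on a scan where its size is still acceptable for CR. The protocol limits size for new nodes, for baseline selection and for CR, but not for regrowth of a followed node.

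The exposure is selective: the deeper the nodal response, the fewer millimetres of growth, or of reading variation, end it. For liver and spleen, 10.4 asks for an unequivocal increase. The node bullet has no such qualifier, no repeat scan is required to confirm PD, and no central reader would catch a marginal call.

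What is at stake first is response duration, where the nadir reference is written down. If sites or programmers carry that reference over to PD generally, PFS and the 8-week confirmation of PR are affected as well, and PR feeds the primary endpoint.

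**Working it through.** **1. The plan's own equivalence.** Section 10.4 equates a 50% rise in greatest diameter with a rise above 65% in the bidimensional product. This does not hold in general:
- Both axes up 50%: 1.5² − 1 = 125%.
- Long axis only: 50%, so 6 x 6 to 9 x 6 mm meets the diameter limb but not the product limb.
- Equal growth reaches 65% in product at √1.65 − 1 = 28.5% in diameter, that is 6 mm to 7.7 mm.

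This is a separate problem. Resolving it either way leaves the missing size limit in place. The rest uses the 50% diameter limb.

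**2. Overlap of PD and CR.** With the nadir as reference, the PD size is 1.5 x nadir. The node stays within the CR limit while 1.5 x nadir ≤ 15 mm, that is nadir ≤ 10 mm.

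| Nadir (mm) | PD from (mm) | Growth needed (mm) | Within 15 mm CR limit? |
|---|---|---|---|
| 2 | 3 | 1 | yes |
| 5 | 7.5 | 2.5 | yes |
| 6 | 9 | 3 | yes |
| 10 | 15 | 5 | yes |
| 12 | 18 | 6 | no |
| 20 | 30 | 10 | no |
| 30 | 45 | 15 | no |

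No assumption about measurement error enters here.

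**3. Dependence on the reference.** Followed nodes exceed 15 mm at baseline (10.2). With baseline as reference, PD needs more than 1.5 x 15 = 22.5 mm and the overlap disappears. The result therefore holds where the nadir reference is written (10.5 and the SAP) and is conditional elsewhere.

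**4. Illustration of false PD.** Assumptions, none from the documents: a stable node of true size d; independent normal reading error with the same SD at each scan; one nadir scan and one later scan. PD is called when the second reading is at least 1.5 times the first. The variance of (second − 1.5 x first) is SD² x (1 + 1.5²) = 3.25 SD², so

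q = 1 − Φ(0.5 d / (SD x √3.25)), and for any of six nodes, 1 − (1 − q)⁶.

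| d (mm) | SD (mm) | 0.5d / (SD√3.25) | One node | Any of six |
|---|---|---|---|---|
| 6 | 0.75 | 2.219 | 1.3% | 7.7% |
| 6 | 1.0 | 1.664 | 4.8% | 25.6% |
| 6 | 1.5 | 1.109 | 13.4% | 57.7% |
| 20 | 1.5 | 3.698 | 0.01% | 0.07% |

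If the reference is a 5 mm default entry it has no reading error. For a true size of 5 mm and SD 1.0 mm, q = 1 − Φ(2.5 / 1.0) = 0.6%, and for six nodes 3.7%.

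Six nodes all sitting at 6 mm is an extreme case, and readings within one patient are unlikely to be fully independent. The contrast between small and large nodes is firmer than any single percentage.

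**5. Default entries.** From 0 mm a percentage increase is undefined. From a 5 mm default, a later 8 mm reading is +60%, but the entry stands for a lesion too small to measure while the PD bullet speaks of measurable nodes. The text does not say whether the 50% rule or the new-node rule governs either case.

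**The case against.** **The reference is not set for PD in general.** This stands. A reader might infer that small-node variation cancels confirmed-pending PRs, shortens PFS and can overturn the rule of 2 responses in 12. The documents do not support that as stated, because neither the PD and PR text in 10.4 nor 10.7 names a reference. Even under a nadir reference, a reversal needs exactly two responders with one lost in this way. PR also requires only a 50% nodal reduction, or a fall in lymphocytes, so many responders would never have nodes of 10 mm or less. The design calculation itself is sound: stopping on 0 of 5 and rejecting at 2 of 12 gives type I error 0.084 and power 0.802. The documents give no basis for an assumed fraction of lost responders.

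**A node returning from 0 mm.** A reader might infer that 0 mm to 4 mm is PD. It is not stated to be; judged as a new node, 4 mm would fall well short of the limit. The right description is unresolved.

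**The secondary endpoints are descriptive.** True: the SAP reports the median and range of response duration and a Kaplan–Meier plot of PFS. A bias in a descriptive estimate is still a bias, but no test depends on it.

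**The definitions follow cited workshop criteria, so a size floor is a design preference.** Partly fair. The inconsistency, however, lies within this protocol's own CR, PD and measurement rules, and can be settled with a limit it already contains.

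**A floor delays recognition of true regrowth.** Correct, and a real cost: a 6 mm node would need to grow by more than 9 mm instead of 3 mm.

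**Conclusion.** The concern holds for response duration. As written, a followed node with a nadir of 10 mm or less can be PD while within the CR nodal limit, and the triggering growth falls in proportion to the nadir. That follows from the text and simple arithmetic. For PFS and PR confirmation the defect is an unstated reference: the same exposure follows if the nadir is used and vanishes if baseline is used. For 0 mm and 5 mm default entries, the governing rule is missing.

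The likely frequency cannot be derived from the documents. Under the stated error model it runs from about 1% to 13% per scan pair for a single 6 mm node and is negligible at 20 mm. This should be corrected before endpoints are classified; it does not invalidate the design.

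**What to change.** For endpoint classification:

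1. State in 10.4 and 10.7 that progression is judged against the smallest on-study measurement, in line with 10.5.
2. Add to the recorded-node PD bullet that the node must also exceed 1.5 cm in greatest diameter at that scan. This is the CR nodal limit; the limit for new and followed nodes is two-dimensional and not identical. No node can then be both CR-compatible and PD.
3. State that regrowth from a 0 mm or 5 mm default entry counts only once it exceeds that limit.
4. Carry the same wording into the SAP for Table 13 and Figure 2.

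**Cost.** A few clauses and a programming check. Measurements are already recorded, so no new data are needed. Nodes with a nadir above 10 mm are unaffected, since 1.5 x nadir already exceeds 15 mm. Regrowth of a deeply shrunken node may be dated a scan interval later (8 weeks up to week 24, 12 weeks after that), or more if regrowth is slow, which slightly lengthens response duration and PFS.

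Because section 12.2 takes patients off study at progression, the sponsor should reconcile that section with the clarified endpoint definition. No treatment-stopping rule is proposed here.

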9.1 Evaluation During Protocol Treatment

[figure not shown]
Investigations		Timing		
History and Physical Exam including:	
 History Weight ECOG Performance status Blood pressure and pulse Clinical tumour / organomegaly measurements (if applicable) 	Day 1 each cycle		
Hematology ¹	CBC, differential (including lymphocytes)			
Biochemistry ¹	
 
  
 creatinine potassium bilirubin (fractionated if known Gilberts) LDH AST, ALT 	 
 calcium albumin glucose (fasting)⁵ phosphate⁶ uric acid⁶ lipase 	
 
	
 creatinine potassium bilirubin (fractionated if known Gilberts) LDH AST, ALT 	
 calcium albumin glucose (fasting)⁵ phosphate⁶ uric acid⁶ lipase 	Days 1 and 14 cycle 1 and 2 ² Day 1 each cycle thereafter ² Tumour lysis monitoring on days 1, 2, and 3 of cycle 1 required only in first 4 patients treated, see below ⁶

 creatinine potassium bilirubin (fractionated if known Gilberts) LDH AST, ALT 	
 calcium albumin glucose (fasting)⁵ phosphate⁶ uric acid⁶ lipase 			
Radiology ³	
 CT scan of neck, chest, abdomen and pelvis 	
 To be repeated 8, 16, and 24 weeks from registration and thereafter every 12 weeks⁷. At time PR or CR criteria are otherwise met and 8 weeks after PR or CR to confirm. 		
Assessment for Minimal Residual Disease (MRD) (Optional)	
MRD assessment either by:
 
 4-color Flow Cytometry (MRD Flow) or Allele Specific Oligonucleotide PCR on peripheral blood or Flow cytometry or immunohistochemistry on bone marrow 	Desirable if CR criteria otherwise met, but optional.		
Bone Marrow	
 Bone marrow aspirate and biopsy 	At time other criteria for CR first met and 8 weeks later to confirm sustained CR or if cytopenia of uncertain cause.		
Correlative blood work	
 Whole blood processed as per Section 17 and Laboratory Manual 	At time of disease progression (if applicable)		
Mood Questionnaire	
 Patient self-rating mood scales for depression (PHQ-9) and anxiety (GAD-7) 	Days 1 and 14 cycle 1 and 2, Day 1 of each cycle thereafter and end of treatment visit		

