9.3 Evaluation After Protocol Treatment

All patients will be seen 4 weeks after the end of the last cycle (4 Week Post Treatment Report).

Patients whose treatment is permanently discontinued due to an adverse event or non-hepatic clinically significant laboratory value, should be followed as clinically indicated until resolved to \leq grade 2. See Section 8.4.3 for more detailed guidance on patients who discontinue study treatment due to hepatic toxicity.

Follow-up beyond the 4 week treatment report is not required for patients who go off protocol treatment with progressive disease, except to document ongoing toxicities (until resolved to \leq grade 2), late toxicities (including second malignancies) and death if within 30 days of last dose.

For patients who go off protocol treatment with objective CR, PR or SD ongoing, follow up including response assessment will be required every three months until relapse/progression (Follow-Up Report). If the patient starts new anticancer therapy, contact the study coordinator to discuss whether further follow-up is required.

For patients who go off protocol therapy with suspected PR or CR, an 8 week confirmatory response assessment including CT scanning will be required as per Sections 9.1 and 10.4, if not already performed.

A Death Report is only required if death occurs within 30 days of last dose or if patient dies before progression/relapse; due within 2 weeks of knowledge of death (see Appendix IV –Documentation for Study).

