12.2 Duration of Protocol Treatment

(see Section 10.0 for response definition)

- For patients who achieve a complete or partial response, therapy will continue until objective disease progression or unacceptable toxicity, whichever occurs first.
- For stable patients, therapy will continue for a maximum of 6 cycles (24 weeks). Patients who have no evidence of tumour shrinkage at this point should go off therapy and receive other treatment at the investigator's discretion.
- Patients who progress (treatment failure) will go off study at the time progression is documented clinically and/or radiographically.

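### The nodal progression rule equates a 50% diameter increase with a 65% product increase; the conversion is wrong and can err in either direction

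*Protocol*

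**What the plan says.** Under progression of lymphadenopathy, protocol section 10.4 gives two routes. One is a new lesion, such as a new enlarged node above 1.5 x 1.5 cm. The other is growth of any node already recorded as measurable: "An increase by 50% or more in greatest determined diameter (= greater than 65% increase in bidimensional product"). Meeting any single progression criterion is enough.

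Elsewhere in 10.4, nodal shrinkage for partial response (Group A) may be judged "either in the sum products of up to 6 measurable lymph nodes, or in the largest diameter". A partial response must also last at least 8 weeks "in the absence of any criteria definitive of progressive disease".

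Progression then drives several things:
- Stopping (12.2): "Patients who progress (treatment failure) will go off study at the time progression is documented clinically and/or radiographically".
- The end of response duration (10.5) and the PFS event (10.7).

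On-treatment CT is scheduled in 9.1: "To be repeated 8, 16, and 24 weeks from registration and thereafter every 12 weeks". Section 13.1 provides no central radiology review. The SAP does not define progression. It reports response duration as a median with range and PFS as a Kaplan-Meier plot.

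**The concern.** A change in one diameter does not determine the change in the product of two diameters; that depends on the other axis. By joining the two figures with an equals sign, the protocol tells sites that they are interchangeable. Sites have both axes to hand, because section 10.2 sizes nodes in two dimensions and the response rule uses products. If the two figures disagree, two sites that both follow the text can classify the same node differently. One patient then comes off treatment with a PFS event and the other continues.

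**Working it through.** **Inputs.** From 10.4: diameter threshold at least +50%, product threshold above +65%, applied to any one recorded node. From 9.1: scans at weeks 8, 16 and 24.

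**Formula.** If the long axis changes by a and the short axis by b, the product changes by (1 + a)(1 + b) - 1. This holds whether the reference size is baseline or a later minimum.

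**Step 1: try to reproduce 65%.** Set a = 0.50.

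| Short-axis change b | Product change |
|---|---|
| 0% | 1.5 x 1.00 - 1 = +50% |
| +5% | 1.5 x 1.05 - 1 = +57.5% |
| +10% | 1.5 x 1.10 - 1 = +65% |
| +25% | 1.5 x 1.25 - 1 = +87.5% |
| +50% (same shape) | 1.5 x 1.50 - 1 = +125% |

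Solving 1.5(1 + b) = 1.65 gives b = 10%. The stated figure is reproduced for that one growth shape only. A volume scale does not give it either: 1.5^3 - 1 = +237.5%.

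**Step 2: invert it.** Under uniform growth, +65% product is sqrt(1.65) - 1 = +28.5% per diameter, well short of +50%.

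**Step 3: nodes on which the two figures disagree.**

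| Node (cm) | Diameter | Product | Progression by |
|---|---|---|---|
| 2.0 x 2.0 to 2.6 x 2.6 | +30% | 6.76/4.00 - 1 = +69% | product only |
| 3.0 x 2.0 to 4.5 x 2.0 | +50% | 9.0/6.0 - 1 = +50% | diameter only |

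When the long axis reaches +50%, the product figure has already been passed if the short axis has grown by more than 10%, and has not been if it has grown by less.

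**Step 4: what this could do to a progression date (illustration only).** Assume steady exponential uniform growth from baseline, no other progression criterion, and the three fixed scans only. If the product passes +65% at week t, the diameter passes +50% at week t x ln(1.5)/ln(sqrt(1.65)) = t x 0.4055/0.2504 = 1.619t. Each crossing is seen at the next scan. The cut points are 8/1.619 = 4.9, 16/1.619 = 9.9 and 24/1.619 = 14.8 weeks.

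| t (weeks) | Scan, product | Scan, diameter | Difference |
|---|---|---|---|
| up to 4.9 | 8 | 8 | 0 weeks |
| 4.9 to 8 | 8 | 16 | 8 weeks |
| 8 to 9.9 | 16 | 16 | 0 weeks |
| 9.9 to 14.8 | 16 | 24 | 8 weeks |
| 14.8 to 16 | 16 | not by 24 | not defined |
| 16 to 24 | 24 | not by 24 | not defined |

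Linear growth moves the cut points to 4.55, 9.10 and 13.66 weeks (ratio 0.5/0.2845 = 1.757). The difference is again 0 or 8 weeks when both thresholds are crossed by week 24.

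In the last two rows, any difference depends on later assessments. Treatment is capped: "For stable patients, therapy will continue for a maximum of 6 cycles (24 weeks"). After that, "follow up including response assessment will be required every three months until relapse/progression", subject to "If the patient starts new anticancer therapy, contact the study coordinator to discuss whether further follow-up is required". No figure can be given there.

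The order in this table follows from assuming uniform growth. If only the long axis grows, the product reaches +65% after the diameter reaches +50%, at ln(1.65)/ln(1.5) = 0.5008/0.4055 = 1.235 times the elapsed time. The product figure is then the later one.

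**The case against.** **Diameter plainly governs.** It is the main clause and the product figure is a gloss. Where 10.4 means true alternatives it says so, as in Group A of partial response. Section 10.8 also works with longest diameters when lesions split or merge. This stands as the better reading, and most sites would probably follow it. It is still an inference, because no section says which figure prevails. The nodal case report form and the data guidebook might steer sites one way, but they are not in the documents.

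**The coordinating group can put it right.** Lesion measurements are recorded at each evaluation (10.8) and radiology reports are uploaded (Appendix IV), so progression dates could be re-derived on diameter. This stands in part. It cannot restore treatment stopped early or scans never done. Section 13.1 rules out central radiology review. A reader might infer that site calls go unchecked, but that section does not say so.

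**Little turns on it.** Other criteria, such as a new node or organ enlargement, may establish progression anyway. PFS and response duration are secondary and descriptive, with no test attached. This stands, and it sets the severity.

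**Conclusion.** The rule is wrong as written, and the point is minor. The equality fails for every growth shape except a short axis growing by 10% while the long axis grows by 50%. This conclusion is pure geometry and needs no assumption about the patients. The consequence arises only if a site applies the product figure. Treatment stopping, PFS and response duration can then move in either direction.

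Three stronger readings are tempting, and the documents do not support them:

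- *That the error brings progression forward and so shortens PFS.* This follows only if the short axis typically grows by more than 10% when the long axis grows by 50%. The documents say nothing about growth shape or about how many nodes would be discordant, so the net direction is unknown.
- *That progression dates shift by 8 weeks.* The 0-or-8-week result rests on one hypothetical growth model with steady growth from baseline. It does not describe patients whose nodes first shrink, so it says nothing about response duration.
- *That the primary endpoint is at risk because 2 responses in 12 reject the null hypothesis.* A response would be lost only if a patient otherwise in partial response had a discordant node before the 8-week confirmation and met no other progression criterion. That is possible but remote, and no frequency is available.

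**What to change.** In section 10.4, delete the parenthesis giving the 65% product equivalent. Growth of a node already recorded as measurable is then judged only by an increase of at least 50% in its greatest diameter, wherever progression is used: stopping, PFS and response duration. Every other progression criterion stays unchanged, including new enlarged nodes above 1.5 x 1.5 cm under the same heading. Diameter would therefore not become the only route to nodal progression.

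The cost is one deletion in the protocol. No new data are needed, and the sample size, scan schedule and endpoints are untouched.
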